7.2 Exclusion Criteria

There are no exclusion criteria for the HIV provider survey. Individuals will be excluded from the pilot study participation if they:

Have a serious medical, psychiatric or substance use disorder that, in the opinion of the study physician, would make study participation hazardous to the participant, compromise study findings, or prevent the participant from completing the study.

Examples include:

- 1) Disabling or terminal medical illness (e.g., active opportunistic infection, uncompensated heart failure, cirrhosis or end-stage liver disease, acute hepatitis and moderate to severe renal impairment) as assessed by medical history, review of systems, physical exam and/or laboratory assessments;
 - a) Severe, untreated or inadequately treated mental health disorder (e.g., active psychosis, uncontrolled manic-depressive illness) as assessed by history and/or clinical interview;
 - b) Current severe benzodiazepine or other depressant or sedative hypnotic use requiring medical detoxification;
 - c) Suicidal or homicidal ideation requiring immediate attention.
- 2) Have aspartate aminotransferase (AST) or alanine aminotransferase (ALT) liver enzymes greater than 5 times upper limit of normal on screening phlebotomy. Results from tests conducted within the past 30 days which are abstracted from medical record information are acceptable.

- 3) Have INR > 1.5 or platelet count <100k. Results from tests conducted within the past 30 days which are abstracted from medical record information are acceptable.
- 4) Have known allergy or sensitivity to naloxone, naltrexone, polylactide-co-glycolide, carboxymethylcellulose, or other components of the Vivitrol® diluents.
- 5) Anticipate undergoing surgery during study participation.
- 6) Have chronic pain requiring ongoing pain management with opioid analgesics.
- 7) Pending legal action or other reasons that might prevent an individual from completing the study.
- 8) Currently pregnant or breastfeeding.
- 9) Body habitus that, in the judgment of the study physician, precludes safe intramuscular injection of XR-NTX, (e.g. excess fat tissue over the buttocks).
- 10) Received methadone or buprenorphine maintenance therapy for treatment of opioid dependence in the 4 weeks prior to screening.
- 11) Have taken an investigational drug in another study within 30 days of study consent.
- 12) Have ECG findings that, in the opinion of the study medical clinician would preclude safe participation in the study. Results from ECGs conducted within the past 30 days which are abstracted from medical record information are acceptable.
- 13) Have had treatment with XR-NTX for opioid or alcohol dependence in the 3 months prior to screening.

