we will survey HIV-infected patients regarding attitudes toward opioid antagonist therapy (Aim 2), track rate of participant recruitment (Aim 3), and randomize those who have untreated opioid and/or alcohol use disorders to receive XR-NTX vs. TAU (Aim 4). Participants will attend study visits every 4 weeks for 16 weeks. Treatment initiation will be assessed at 4 weeks and retention at 16 weeks (4 XR-NTX injections). Randomization will continue until a maximum of 50 participants or 12 months are reached. Pilot study duration will be a maximum of 17 months (maximum 12 months recruitment + 5 months study participation for those enrolled at the end of the recruitment period). We will assess feasibility of a multi-site trial of XR-NTX vs. TAU by addressing four pilot study specific aims.

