Aim 4: Assess the feasibility of integrating XR-NTX for opioid and alcohol use disorders into HIV clinics. Data collection during study start-up will inform selection of 2 HIV clinics to implement XR-NTX treatment. HIV providers and staff will be trained in detoxification and XR-NTX induction and management. HIV-infected subjects with untreated opioid and/or alcohol use disorders will be randomized to XR-NTX or TAU, followed by detoxification (if needed) and treatment induction. The primary outcomes are 1) treatment initiation (successful treatment initiation of XR-NTX or TAU within 4 weeks of randomization), and 2) retention on treatment condition at 16 weeks. Secondary outcomes include change in 1) HIV-1 RNA viral suppression, 2) Illicit drug and alcohol use, 3) HIV care engagement (receipt of ART, HIV visit adherence, ART adherence), and safety (percent with precipitated withdrawal, hepatotoxicity, or overdose).

Aim 4 Pilot Objective A: Estimate effect size point estimates for rate of treatment initiation and 16 week retention among HIV-infected patients with alcohol or opioid use disorders randomized to XR-NTX vs. TAU.

Aim 4 Pilot Objective B: Estimate effect size point estimates for secondary outcomes of HIV-1 RNA viral suppression, illicit drug and alcohol use, HIV care engagement, and safety among HIV-infected patients with alcohol or opioid use disorders randomized to XR-NTX vs. TAU.

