7.0 STUDY POPULATION

7.1 Inclusion Criteria

Participating individuals in the provider acceptability survey are HIV providers, defined as any physician, nurse practitioner, or physician assistant who serves as primary HIV provider for HIV- infected patients at least one half day per week.

Individuals participating in the pilot study must:

- 1) Meet DSM-5 criteria for moderate or severe opioid use disorder and/or alcohol use disorder.
- 2) Be willing to be randomized to antagonist-based therapy or TAU for treatment of opioid and/or alcohol use disorders.
- 3) Be HIV-infected as defined by history of positive HIV serology or HIV RNA pcr > 10,000 copies/mL).
- 4) Be willing to establish ongoing HIV care at CTP if not already receiving ongoing care.
- 5) Be willing to initiate ART if not already prescribed ART, regardless of CD4 count.
- 6) Be at least 18 years old.
- 7) Be able to provide written informed consent and HIPAA (if applicable) for medical record abstraction.
- 8) Be able to communicate in English.
- 9) If female, be willing to take measures to avoid becoming pregnant.

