7.7 Rationale for CTP Selection

We will use the same site selection criteria for the pilot study as is planned for the multisite study. Sites will be selected for participation that have an adequate number of HIV-infected participants with untreated opioid use and/or untreated alcohol use disorders. In order to achieve target enrollment for this study, which is approximately 25 participants per site over 12 months of enrollment, we expect that participating HIV clinics will need to see $\geq 1,000$ unduplicated HIV-infected potential participants per year. This number is based on estimates of the percent of HIV-infected patients in 17 HIV clinics that were informally queried regarding participant availability (Appendix C), and experience of CHOICES investigators in enrolling subjects in the BHIVES study (Altice, Bruce et al. 2011). We have also included site selection criteria that attempt to limit site variability in treatment effects (e.g., capacity for prescribing ART regardless of CD4 count, presence of on-site addiction counseling services).

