13.6 Treatment Services Review (TSR), Version 6 (28 days)

Select items from the Treatment Services Review, Version 6 (TSR-6) addiction treatment modules will be used to collect data on the number of counseling sessions attended in the past

28 days, as well as detoxification, outpatient, inpatient, and medication-assisted addiction treatment services (Cacciola, Alterman et al. 2008). Participants will complete TSR-6 at baseline, treatment initiation, and 4, 8, 12, and 16 weeks (or end-of-medication/end-of-treatment if medication or TAU intervention stopped early) for assessment of TAU and counseling exposure in both TAU and XR-NTX arms.

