17.1 Primary Outcome Measures

Primary outcome variables for the CHOICES pilot study are:

- 1) HIV provider willingness to prescribe XR-NTX (Aim 1): HIV provider willingness to prescribe opioid antagonist treatment will be assessed with measures adapted from the Medical Opinion Survey (MOS) in the provider survey (mean; survey data).
- 2) Patient acceptance of opioid antagonist therapy (Aim 2): HIV-infected patient acceptance of opioid antagonist treatment will be assessed with measures adapted from the Medical Opinion Survey (MOS), administered during participant recruitment. Patients will be asked whether they are willing to participate in a trial of XR-NTX vs. TAU (binary; survey data).
- 3) Rate of participant recruitment into trial (Aim 3): Number of participants randomized in pilot study per 12 months. This will be used to estimate the speed at which a multisite trial could enroll participants. The number of participants randomized will be assessed on a monthly basis until either 50 participants have enrolled, or 12 months of recruitment have elapsed, whichever comes first (rate; randomization data).
- 4) Treatment initiation (Aim 4A): Treatment initiation is defined as receipt of at least one dose of study medication for those randomized to XR-NTX within 4 weeks of randomization. For those randomized to TAU, treatment initiation will be defined as receiving at least one dose of medication-assisted therapy other than XR-NTX (e.g., buprenorphine for opioid use disorder, disulfiram for alcohol use disorder), or attendance on at least 1 day of non-medication-assisted therapies (e.g., 12-step groups, outpatient rehab referral, etc.) within 4 weeks of randomization. Treatment initiation will be assessed with weekly phone calls from research staff until treatment is initiated or 4 weeks from date of randomization have elapsed, as which point a participant will be considered to have failed treatment initiation. (binary; chart review and self-report).

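### The protocol describes an untreated population but admits people already in other treatment, so outcome 4A mixes continuing with new treatment in the TAU arm only

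*Protocol*

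**What the plan says.** **Population.** The Protocol synopsis (2.0) says the study will "randomize those who have untreated opioid and/or alcohol use disorders to receive XR-NTX vs. TAU". Aim 4 (2.1) repeats it: "HIV-infected subjects with untreated opioid and/or alcohol use disorders will be randomized to XR-NTX or TAU". Section 7.7 wants sites with an "adequate number of HIV-infected participants with untreated opioid use and/or untreated alcohol use disorders".

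**Criteria.** Inclusion criterion 1 in 7.1 asks only for a diagnosis: "Meet DSM-5 criteria for moderate or severe opioid use disorder and/or alcohol use disorder". Two exclusions in 7.2 concern earlier treatment of the disorder. Number 10 reads "Received methadone or buprenorphine maintenance therapy for treatment of opioid dependence in the 4 weeks prior to screening" and number 13 reads "Have had treatment with XR-NTX for opioid or alcohol dependence in the 3 months prior to screening". None concerns disulfiram, acamprosate, oral naltrexone, counseling, rehabilitation or 12-step groups.

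**Outcome 4A (8.1 item 4, 17.1 item 4).** In the XR-NTX arm, initiation is at least one study injection within 4 weeks of randomization. In the TAU arm it is one dose of any addiction medication other than XR-NTX, or "attendance on at least 1 day of non-medication-assisted therapies (e.g., 12-step groups, outpatient rehab referral, etc.) within 4 weeks of randomization". Nothing requires the TAU treatment to be new.

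**Background care and data.** Both arms keep their usual clinic addiction counseling (9.3.1), and every site must offer it (6.1, 7.6). Earlier treatment is recorded: "Participants will complete TSR-6 at baseline, treatment initiation, and 4, 8, 12, and 16 weeks" (13.6). The medication-assisted treatment items (13.7) are also taken at baseline. Both look back 28 days. The 4A definition uses neither.

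**The concern.** The eligibility rules and the scoring rule interact. For alcohol use disorder, XR-NTX is the only earlier treatment that 7.2 washes out. The psychosocial treatments that 4.3 and 9.3.4 describe as usual alcohol care are left open. A participant who already attends weekly meetings is therefore a TAU success at the next routine meeting, without starting anything. In the XR-NTX arm, that attendance does not count.

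Randomization balances the share already in treatment, but it cannot balance a rule that scores that share differently by arm. A larger sample would not help either.

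Objective 4A (5.1) compares the arms, and Aim 4 Objective A wants effect-size estimates to plan a multi-site trial. If readers take the TAU figure as the rate at which untreated patients start treatment, it may be too high. Only initiators are assessed for retention, so continuing participants also enter the TAU side of 4B, where they sit alongside people who have just started.

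**Working it through.** **1. The plan's own precision figure.** Table 17.2.1 gives a 20th-percentile sample size of 48 and a 95% half-width of 0.21 for the initiation probability (2.28 per site-month, 2 sites, limits of 50 participants and 12 months). Poisson recruitment with mean 2.28 × 2 × 12 = 54.72, capped at 50, has a 20th percentile of 48, or 24 per arm. The exact binomial half-width at a proportion of 0.5 with 24 participants is 0.209. The figure reproduces. It describes random error only and does not cover the shift below.

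**2. Who is admitted and how they are scored.**

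| Treatment at baseline | Excluded by 7.2? | One more dose or session: TAU arm | Same, XR-NTX arm |
|---|---|---|---|
| Methadone or buprenorphine maintenance within 4 weeks | Yes | – | – |
| XR-NTX within 3 months | Yes | – | – |
| Disulfiram, acamprosate, oral naltrexone | No | Initiated | Not initiated |
| 12-step, rehabilitation, counseling | No | Initiated | Not initiated |

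The general clause in 7.2 on conditions that could compromise study findings concerns serious medical, psychiatric or substance use disorders. It does not address current treatment, so it does not close the gap.

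**3. Size of the shift.** Let f be the share of TAU participants already in a qualifying treatment and p the new-initiation rate among the rest. If everyone already in treatment continues for at least one session or dose:

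- counted TAU rate = f + (1 − f)p
- shift relative to p = f + (1 − f)p − p = f(1 − p)

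The documents give neither f nor p, so these values are assumptions:

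- p = 0.60, f = 0.10: 0.10 + 0.90 × 0.60 = 0.64, a shift of 4 points
- p = 0.60, f = 0.20: 0.20 + 0.80 × 0.60 = 0.68, a shift of 8 points
- p = 0.60, f = 0.40: 0.40 + 0.60 × 0.60 = 0.76, a shift of 16 points
- widest range tried: 0.10 × 0.30 = 3 points (f = 0.10, p = 0.70) to 0.50 × 0.60 = 30 points (f = 0.50, p = 0.40)

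With 24 per arm, 4 points is 0.04 × 24 ≈ 1 participant and 8 points is about 2. If only a fraction c continue, and the others start something new at rate p, the shift falls to fc(1 − p).

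**4. Effect on the apparent direction.** Take true new initiation of 0.50 in both arms and 25 per arm. With f = 0, TAU shows the strictly higher rate with probability (1 − tie probability)/2 = (1 − 0.112)/2 ≈ 0.44, where the tie probability is C(50,25)/2^50. With f = 0.10 this becomes 0.58, and with f = 0.20 it becomes 0.72.

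**5. Check on the obvious remedy.** Suppose TAU initiation counted only treatment not received before baseline, and people already in treatment start something different with probability q. The counted rate is then fq + (1 − f)p. With f = 0.40, p = 0.60 and q = 0, it is 0.60 × 0.60 = 0.36, which is 24 points below p. That error is larger than the 16-point shift it would replace, and it would also remove those participants from 4B.

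**The case against.** The strongest reply is that TAU is a strategy. For a patient already in counseling or a 12-step group, usual care may simply continue, and counting it answers a fair pragmatic question: is the participant receiving the assigned approach within 4 weeks? A reader might infer from the asymmetry that 4A always favours TAU. The documents do not support that. The shift is a bias only if the target is new initiation. What stands against the reply is the protocol's own wording: if continuing care is meant to count, then *untreated* and *initiation* are the wrong words and the sections still conflict.

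A reader might also infer a large distortion, close to the 0.21 half-width. That needs f of about 0.40, for which the protocol offers no support. Section 4.1 says only a minority of such patients receive addiction treatment and that medication for alcohol use disorder is uncommon in HIV clinics; 4.3 and 9.3.4 call it rare. The gap is therefore mainly psychosocial, and f may be modest.

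The study is also a pilot of at most 50. Section 17.3 estimates 4A separately by arm with exact intervals and specifies no between-arm test, so no confirmatory claim depends on it. That limits the consequence.

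Finally, a breakdown by baseline treatment is ordinary SAP content and may be planned there. That is fair for the breakdown. It does not cover the population description or the 4A definition, both of which are fixed in the protocol.

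**Conclusion.** The point holds in limited form. The population is described as untreated in three places, but 7.2 excludes only recent methadone or buprenorphine maintenance and XR-NTX. The 4A rule then counts continuing treatment as initiation in TAU and not in XR-NTX. Both facts are in the text.

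Against a target of new initiation, the TAU rate moves upward by f(1 − p): 4 to 8 points at p = 0.60 and f = 0.10 to 0.20, and more if f is larger. This assumes that everyone already in treatment continues for at least one dose or session, and both f and p are assumed. The same people enter the 4B set; the documents do not show in which direction that moves retention.

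The documents do not support saying that 4A is invalid, that the distortion is known to be large, or that TAU initiation should be restricted to new treatment alone. This is a should-fix point, with moderate confidence in its size.

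**What to change.** 1. Reconcile the population description in 2.0, 2.1 (Aim 4) and 7.7 with the criteria in 7.2. Either define *untreated*, or state that people in current psychosocial or other non-excluded treatment are eligible.
2. In 8.1 item 4 and 17.1 item 4, classify each TAU initiation as new (a treatment not received in the 28 days before baseline) or continuing, using the baseline TSR-6 and medication-assisted treatment items. Add oral naltrexone to the list in 13.7, which omits it although 9.3.4 names naltrexone as an alcohol medication. Confirm that 12-step attendance is captured, since 13.6 does not name it.
3. Report 4A in both arms by baseline treatment status, with the new-initiation and any-treatment rates side by side. Do not score continuing TAU recipients simply as failures.

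The cost is small: changes of wording, one added medication item, possibly one added attendance item, and slightly more analysis. The subgroups will be small with 24 or 25 per arm, and the new-initiation figure for TAU will look less favourable than the present one. Recruitment is unaffected unless the sponsor defines *untreated* more narrowly than 7.2 now does.

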7.3 Recruitment

HIV Provider Survey Recruitment:

HIV providers are recruited from HIV practices to complete anonymous surveys regarding attitudes toward medication-assisted treatment for alcohol and opioid use disorders. Medical directors of 15- HIV clinics will provide email addresses of HIV providers at their clinic and encourage all clinic HIV providers to complete an anonymous web-based survey.

Pilot Study Recruitment:

Study participants are recruited from participating HIV outpatient clinics, which will serve as CTPs for CTN-0055. HIV clinics likely to participate in CTN-0055 typically serve as patient-centered medical homes for HIV-infected participants, offering a broad array of on-site case management, social work, and counseling support services to engage and retain patients in care. All members of the HIV clinic care team will be educated regarding the study and asked to refer potential participants who are interested in learning more about the study to clinic research staff for screening. The CTP PI will either be an attending HIV provider in the HIV clinic or have strong relationships with HIV providers, so we anticipate excellent cooperation in approaching potential participants. Because the study seeks to improve engagement in HIV care, the HIV clinic care team and research staff will interact with community-based outreach services to identify and engage potential participants who are new to HIV care. If a participant is interested in learning more about the study, a study staff member will meet with the participant to discuss the study. Potential participants will be briefly instructed regarding opioid agonist and antagonist therapy and complete a survey demonstrating understanding as part of the consent process prior to enrollment. Specific recruitment procedures (e.g., local educational activities, community outreach, print and web-based advertisements, etc.) will vary by site accordingly to local needs. Strict ethical guidelines regarding professional conduct

and confidentiality will be enforced for all study staff.

Enrolling participants in clinical settings poses many challenges to screening and interviewing potential participants (Berkman, Leipzig et al. 2001; Falcon, Bridge et al. 2011; Korthuis, Saha et al. 2011; Menezes, Eron et al. 2011), including the rapid pace of care, interruptions, clinic productivity requirements, space limitations, participants not feeling well enough, and the presence of multiple HIV care team staff members. To minimize the impact of these challenges, research staff will spend considerable time in participating HIV clinics interacting with staff, familiarizing themselves with clinic patient flow, and learning how to communicate and negotiate with clinic staff regarding the necessary space and time to conduct interviews. Site PIs, who are HIV clinic providers, will facilitate negotiation of space and time requirements and be a resource to research staff regarding participating HIV clinic procedures. Staff and sites with experience and expertise in conducting research studies in outpatient HIV clinic settings will be prioritized for site selection. A review of 13 clinical trials conducted in the University of North Carolina Infectious Disease Clinic suggested that integrating a dedicated research screener in clinic operations facilitates trial enrollment (Menezes, Eron et al. 2011). Our research team has experience successfully integrating clinical trial research teams with outpatient HIV clinic staff, enrolling 82% of HIV providers and 73% of their eligible participants in one recent trial (Korthuis, Saha et al. 2011).

The interviewer will negotiate the location of the interview as necessary to protect confidentiality and respect HIV clinic patient flow. If necessary, the potential participant will be given the option to participate in screening, consent and interview procedures in a nearby exam room or staff/patient lounge if it is unoccupied or to reschedule the interview at another time. If a participant feels ill during the interview, we will stop and reschedule the interview. In our prior experience conducting research interviews in outpatient HIV clinics, we found this level of flexibility achieved high levels of participation and did not impede the flow of usual HIV clinic activities (Korthuis, Saha et al. 2008; Altice, Bruce et al. 2011; Beach, Saha et al. 2011).

7.4 Special Populations to Consider

This study is likely to enroll persons involved in the criminal justice system who are receiving HIV care at participating CTPs. The study will not recruit persons incarcerated/detained in a correctional facility, but will not exclude parolees, probationers.

Those participants who become incarcerated during the course of their involvement with this study will continue to be followed to ensure safety and data integrity. All study interventions (XR- NTX or TAU) will be discontinued while the participant is incarcerated. If necessary for safety and with the permission of the participant, correctional facility officials will be informed of study participation. When possible, participants will be contacted to complete questionnaires and surveys, which would include safety checks. These visits can occur over the telephone or as in-person visit, whichever is more appropriate for the local research site and the correctional facilities' policies. The visits will only occur if confidentiality can be maintained. This generally assumes that in-person visits will be done in private rooms and that recording equipment (regardless of type of visit) can be turned off or destroyed. No biospecimens will be collected (blood or urine) during any visit that occurs with an incarcerated prisoner. Any document that is specifically for an incarcerated participant will be approved by the local IRBs, including contact letters. All local guidelines will be followed, including any required reporting to the IRB or other institution when a participant becomes incarcerated. Appropriate progress notes will be written to ensure complete documentation of any interaction with an incarcerated participant, specifically mentioning confidentiality procedures.

We will request a federal Certificate of Confidentiality. An OHRP Prisoner Research Certification Letter will be filed through the Lead Team's IRB and distributed to the sites for reference only. Sites are responsible, through

their IRB, for obtaining their own OHRP Prisoner Research Certification Letter. The Lead Team's Letter will not cover participants at the local sites.

